 - b. Effects on youth violent antisocial behavior, SUDs, and risky sexual behavior will be more pronounced among males with the MAOA-LPR low activity alleles compared to males with MAOA-LPR high activity alleles, and among both males and females with 2 copies of the high-activity Val allele of the COMT Val158Met polymorphism compared to those with 2 copies of the low-activity met allele or heterozygotes.
 - c. Effects on maternal SUDs will be concentrated among mothers with 2 copies of the Val158 alleles.
 - d. Effects on child outcomes will be more pronounced among youth born to mothers with either 1) the S/S, S/L_G and "L_G/L_G" (low-activity) genotypes of 5-HTTLPR (conferring susceptibility for depression under adversity) or 2) 2 copies of the high activity COMT Val158 allele (conferring susceptibility to compromised ECF and SUDs under conditions of adversity).
8. **(Secondary)** Program effects on adolescent functioning will be explained by its improvement in prenatal health, early care of the child, maternal life-course, and earlier child academic and behavioral functioning.

Examination of Intervention Effects on Subsequent Children

With an administrative supplement, we addressed the following questions focused on subsequent children born within 5 years of the first child. Note that these questions were framed with no specific hypotheses about the degree to which particular subgroups would benefit from the intervention, given that intervention impact on pregnancy planning had been most pronounced on women with higher psychological resources.

1. To what degree does this program improve the health and development of subsequent children in terms of their a) language, academic, and executive cognitive functioning (ECF); b) depression and anxiety; c) failed conduct grades, d) violent behavior and gang membership, and e) arrests, juvenile detentions, and convictions, especially for violent crimes?
2. To what degree does this program reduce subsequent children's risk for HIV infection, including a) use and abuse of substances; b) risky sexual behaviors; c) sexually transmitted infections (STIs) and d) pregnancies?

3. To what degree are the program effects on subsequent children more pronounced for a) males, b) those born to high-resource mothers, and c) those living in the most disadvantaged neighborhoods at registration?

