improving women's prenatal health behaviors, b) the child's subsequent health and development by improving parents' early care of the child (especially reducing child maltreatment), and c) families' economic self-sufficiency by helping parents plan subsequent pregnancies and make informed choices about work, education, and partner relations. Their clinical strategies are informed by theories of human-ecology, attachment, and self-efficacy.^{1,16}

Prenatal Health Behaviors. Prenatal tobacco and alcohol exposure increase the risk for fetal growth restriction,²⁶ preterm birth,²⁶ and neurodevelopmental impairment (e.g., attention-deficit disorder, cognitive and language delays).²⁷⁻³³ Children born with subtle neurological perturbations resulting from prenatal exposure to substances are more likely to be irritable and inconsolable,³⁴⁻³⁶ making it more difficult for parents to care for them effectively. Improved prenatal health thus also helps parents become competent caregivers. The impacts of tobacco and alcohol exposure on birthweight and dysregulated behavior are moderated by genetic vulnerabilities.^{20,21,37} Prenatal tobacco and alcohol use in the Memphis sample, however, were very low, although nurse-visited women, as hypothesized, did have lower rates of pregnancy-induced hypertension. Children exposed to hypertensive disorders of pregnancy and other obstetrical complications are at increased risk for violent aggression during adolescence.³⁸

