Original Sample Characteristics. We invited 1,290 women from the obstetrical clinic of the Regional Medical Center in Memphis to participate. We recruited women <29 weeks pregnant if they had no previous live births, no specific chronic illnesses thought to contribute to fetal growth retardation or preterm delivery, and at least 2 sociodemographic risks: a) unmarried, b) less than 12 years of education, c) unemployed. Eighty-eight percent (1138/1290) completed informed consent and were randomized to 1 of 4 treatment conditions described below. All low-income women in Memphis registered for prenatal care at this clinic, which meant that we enrolled nearly the entire population during the 1990–1991 enrollment period. The study was designed to follow 742 families in two treatment conditions after delivery. 92% of the women were African-American, 98% were unmarried, 67% were <19 years of age at registration, 85% came from households with incomes < federal poverty guidelines, and 9% smoked cigarettes. At randomization, there were no treatment differences in women's background characteristics.

Randomization. After the completion of informed consent and baseline interviews, identifying information on participants was entered into a computer program that randomized women to treatment conditions. The randomization methods were extensions of Soares and Wu.¹⁸² The model on which we based the randomization included 5 classification factors: maternal race, chronological age (4 levels), gestational age at enrollment, employment status of head of household and geographic region of residence (4 regions).

Statistical Power in the Original Design. We conducted power calculations to determine the number and proportion of subjects to assign to treatment and control conditions while minimizing costs in the initial study period (prenatal through child age 2). This allowed disproportionate assignment of women to treatment and control conditions and a reduction in number of families followed into the postnatal phase of the trial. Given high rates of sample retention, the original power calculations hold.

Treatment Conditions

Treatment 1 - Transportation during Pregnancy. The 166 families in this treatment condition received free round-trip taxicab transportation for scheduled prenatal care appointments. This group did not receive any postpartum services or assessments.

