Treatment 2 - Transportation during Pregnancy and Screening during Infancy. The 514 families in this group received: 1) free transportation for scheduled prenatal care; and 2) developmental screening and referral services for the child at the 6th, 12th, and 24th months of the child's life.

Treatment 3 - Transportation and Nurse-Visitation during Pregnancy Only. The 230 families in this treatment condition received: 1) free transportation for scheduled prenatal care; and 2) intensive nurse home-visitation services during pregnancy and one postpartum visit in the hospital before discharge and one postpartum visit in the home. This group did not receive any postpartum services or assessments.

Treatment 4 - Transportation and Nurse-Visitation during Pregnancy and Infancy. The 228 families in this condition received: 1) free transportation for scheduled prenatal care; 2) intensive nurse home-visitation services during pregnancy and through the child's second birthday; and 3) developmental screening and referral services for the child at the 6th, 12th, and 24th months of the child's life.

Program Plan and Implementation

NFP nurses were charged with 1) improving the outcomes of pregnancy by helping women improve their prenatal health; 2) improving children's subsequent health and development by helping mothers and other caregivers provide more competent care of their babies; and 3) improving women's own health and development by helping them develop self-care practices, plan subsequent pregnancies, complete their educations, and find work. The program guidelines included specific activities to support women's protection of their personal health, including eating balanced diets, avoiding use of substances, exercise, hygiene, advocating for themselves with providers of office-based care, and guidance on risky behavior and social relationships.¹ The program guidelines provided extensive support to mothers and other caregivers in their efforts to care well for their children, including promoting "back to sleep" and safe bedding, reducing hazards in the home, regulated and responsive care of the child.^{1,16}

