The home-visitation program was carried out by the Memphis/Shelby County Health Department during a nursing shortage, which contributed to staff turnover during the conduct of the trial. Program designers were minimally involved in program implementation. These features of program implementation, along with registration of nearly the entire population, make this nearly an effectiveness trial on the efficacy/effectiveness spectrum.

Research Activities for Current Phase of Follow Up

The 18-year follow-up study consisted of a longitudinal follow-up of women and firstborn youth who had not declined participation or died before the first child turned 18. A supplement to this grant allowed us to examine the health and development of subsequent children born within the first five years following birth of the first child. The functioning of subsequent children follows the exact same measurement plan followed for firstborn children with the exception of examining high school graduation. For the postnatal phase of the trial, we followed families assigned to treatments 2 (n=514) and 4 (n=228) for primary assessments. As shown in Table 2, which provides the CONSORT information for mothers and first-born children, we have been remarkably successful in retaining the sample through the most recent follow-up. At child age 18, we completed assessments on 618 mothers and 629 youth, for completion rates of 83% of the mothers and 85% of the children originally randomized, and 90% of the mothers and 92% of the children who had not died prior to the 18-year assessment. These assessments do not include an additional 16 cases where the biological mother was not the custodial parent and an interview was conducted with the child's guardian. We discuss CONSORT information for subsequent children in the results section below. Obtaining high rates of sample retention is crucial in ensuring accurate estimates of intervention impact, as simulation analyses of the 12 year follow-up of this trial have indicated that if the sample recruitment efforts had been shut down at 70 or 80% of the originally enrolled participants, the rates of type II errors would have increased.¹⁸³

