The primary analyses made use of general linear model methods and their extensions. The focus was on full model specification to account for all sources of variation, and a full examination of interactions among model factors. The primary classification factors for examination in our models, as determined by our hypotheses and earlier work, include treatments (Control vs. Nurse Visited - T), maternal psychological resources (low versus high – P), and sex of child (S). Standard covariates included an index of household poverty, maternal beliefs associated with child abuse, and for child outcomes, age of the child at the 18-year interview. Genetic analyses included the gene as an additional classification factor and were interacted with treatment status only (see more information below). We employed pared-down versions of full model specification when we had infrequently occurring outcomes (e.g. convictions for interpersonal violence). In general the approach involved beginning with a fully specified model and continuing to eliminate non-significant interactions unless a specific a priori hypothesis forced the interaction term(s) into the model.

Continuous variables were run with a general linear model; dichotomous variables with binomial error distributions; low frequency count variables with negative binomial distributions. For outcomes measured over the life course, the above models were extended to mixed or generalized mixed models to account for correlated data (random effects for time with unstructured variance terms). Subsequent children analyses were also run with mixed or generalized mixed models to account for correlation within the same family. We were interested in the treatment effects for subsequent children alone, as opposed to an overall family effect that would include the first born children.

We employed Cox proportional hazard models²³² for outcomes with a survival component. We present in the tables adjusted hazard rates at age 18 since the vast majority of the sample was interviewed after their 18th birthday but rapidly drops off after this date. The methods used for the mortality analyses can be found elsewhere.¹¹

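### The subsequent-children contrasts condition on a birth after randomisation that the program targets, yet the protocol presents them as program effects

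*Protocol*

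**What the plan says.** **Who was randomised, and when.** In *Original Sample Characteristics* the protocol says: "We recruited women <29 weeks pregnant if they had no previous live births". *Randomization* places allocation after consent and the baseline interview, hence before any later child existed.

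**Who is analysed in the supplement.** *Examination of Intervention Effects on Subsequent Children* says "we addressed the following questions focused on subsequent children born within 5 years of the first child". *Research Activities for Current Phase of Follow Up* repeats the limit: "subsequent children born within the first five years following birth of the first child".

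**How the contrast is described.** Questions 1 and 2 of the supplement ask how far the program improves or reduces outcomes in these children. Question 3b asks whether its effects are larger for children of high-resource mothers. Question 4a asks whether those effects are explained by the program's impact on when and how often later births occurred. *Statistical Models and Methods of Analysis* adds: "We were interested in the treatment effects for subsequent children alone".

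**How it is modelled.** The same section says: "Subsequent children analyses were also run with mixed or generalized mixed models to account for correlation within the same family". The general model factors are treatment, maternal psychological resources (low or high) and child sex. Household poverty, beliefs associated with child abuse and child age are covariates.

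**What the program does to later births.** The nurses' tasks include "helping parents plan subsequent pregnancies and make informed choices about work, education, and partner relations" (*Program Content*) and "helping them develop self-care practices, plan subsequent pregnancies, complete their educations, and find work" (*Program Plan and Implementation*). *Maternal Life-Course*, under Preliminary Studies, reports lower fertility, with effects on fertility outcomes stronger in higher-resource mothers. The supplement repeats that "intervention impact on pregnancy planning had been most pronounced on women with higher psychological resources", but only to explain why it sets no subgroup hypotheses.

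**The concern.** Firstborn children are a sound basis for a randomised comparison because that pregnancy already existed at allocation. Later children are not. Whether a mother contributes a child to the supplement depends on what she did after allocation, and the program sets out to change that.

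If the program altered which mothers had another child within five years, the T4 and T2 children may differ in family background even if the program did nothing for them. A difference between arms could then be partly a difference in who was born, and an absence of difference could hide a real effect. Question 3b is the most exposed, because it concerns the stratum in which the protocol reports the stronger fertility effect.

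**Working it through.** No sample size or power figure is given for this analysis, so the check is mainly one of structure, with a few figures from the protocol.

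**1. The contrast being estimated.** Let S = 1 if a mother has an eligible birth and Y be the later child's outcome. The supplement estimates

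E[Y | T4, S = 1] − E[Y | T2, S = 1].

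Randomisation makes all T4 and T2 mothers comparable. It does not make those with S = 1 comparable unless either (a) the program left S unchanged, or (b) the mothers whose S it changed have children with the same prospects as the rest, given the factors in the model. The protocol asserts neither condition.

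**2. Can the program change childbearing?** Table 1, closely spaced subsequent births through child age 12, whole sample: 0.51 (comparison) and 0.34 (nurse), p = .019.

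- Ratio: 0.34 / 0.51 = 0.667, which reproduces the printed IR of 0.67.
- Difference: 0.51 − 0.34 = 0.17 births per mother.

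So the program can plausibly act on S. The figure is not the effect on S, for two reasons. *Subsequent Pregnancy* defines the count as births within two years of one another, and a lengthened interval can still end inside the five-year window. The count also runs to age 12, so it can include births after the window has closed. The protocol gives no effect on births within five years.

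**3. Is the affected factor prognostic for children?** Table 1, comparison group, age 6:

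| Measure | Whole sample | Low-resource | Difference |
|---|---|---|---|
| KABC composite | 90.24 | 87.64 | 2.60 |
| PPVT | 82.13 | 79.08 | 3.05 |

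Firstborn children of low-resource mothers score lower. A fertility effect that varies with resources could therefore shift the mix of families in one arm. This makes condition (b) doubtful without showing that it fails.

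**4. Does the model repair it?** The random family term addresses dependence between siblings, which affects standard errors and has no bearing on comparability of the arms. The low/high resource factor and the covariates can remove selection on what they measure. They leave variation within each resource level and anything unmeasured.

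**5. Mothers with no start to the window.** Table 2 first-pregnancy losses (miscarriages plus stillbirths):

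- T2: 19 + 5 = 24 of 514 (4.7%).
- T4: 8 + 2 = 10 of 228 (4.4%).

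These mothers have no live first birth from which to date five years. The proportions are similar, but any table of eligible births over all randomised mothers must show them separately.

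**6. Question 4a.** Birth timing and rates are proposed as a mediator. They also decide whether a family is in the analysis. Among included families, everyone has at least one birth in the window, so the mediator has been truncated by the inclusion rule.

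**The case against.** The strongest reply has four parts.

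- **The restriction is stated openly.** It appears twice, the questions carry no directional subgroup hypotheses, and the target is declared to be later children alone. This is true. But naming the analysis set does not say that comparing arms within it lacks the protection of randomisation, and the wording around it remains causal.
- **The disclosure may exist.** *Research Activities for Current Phase of Follow Up* says that CONSORT information for subsequent children is discussed in the results section, and the list of tables names Table 16 (CONSORT) and Table 17 (baseline characteristics of families with subsequent children). None of this is in the supplied text. The point stands, so the absence of a birth comparison cannot be charged to the plan. The subsequent-pregnancy variables were removed as outcomes for this phase, but the protocol describes collecting number, timing and intervals.
- **There is no evidence of selection at five years.** Also true. A reader might infer from the 0.67 ratio that a third of eligible births were removed in T4, or that the supplement's results are biased in a known direction. The documents support neither: the ratio concerns spacing, and no eligibility figure is given.
- **It is a supplement, and detail may sit in a SAP.** The conditional analysis set and the effect wording are fixed in the protocol itself, so the interpretation issue is not deferred. A reader might extend the doubt to the main results. That would be wrong, because the firstborn and maternal comparisons do not condition on a later birth.

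**Conclusion.** The point holds as one of interpretation. The T4 versus T2 contrasts in subsequent children, including question 3b, are conditional on a post-randomisation birth that the program targets, and should not be read as randomised program effects. The adjustment described covers sibling correlation and measured selection only.

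The size and sign of any bias cannot be obtained from the documents, and the bias may be zero. It would be zero if the program did not change which mothers had an eligible birth, or changed it in a way unrelated to child outcome after adjustment. The conclusion rests on the protocol's own account of the program's aims, the timing of randomisation and the reported fertility effects. It does not rest on any estimate of imbalance at five years. The matter is worth correcting in the supplement and does not touch the primary hypotheses.

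**What to change.** 1. In *Examination of Intervention Effects on Subsequent Children* (questions 1 to 4) and in *Statistical Models and Methods of Analysis*, state that these contrasts are conditional on a birth within five years of the first child, that this birth follows randomisation, and that they are not to be interpreted as randomised program effects.
2. From the birth data already collected, report by arm and resource level the proportion of the 514 T2 and 228 T4 mothers with an eligible birth, with the 24 and 10 first-pregnancy losses shown separately. Omit this if Tables 16 and 17 or the CONSORT discussion already provide it.
3. At question 4a, note that birth timing and rates also determine who is analysed, so mediation through them among included families is non-randomised.

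Optionally, a mother-level count of affected subsequent children over all randomised mothers could be added. It answers a different question, because it mixes fertility with child outcomes, and it neither corrects nor bounds the bias.

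The cost is softer conclusions for the supplement and a small amount of tabulation. No new data are needed, and the five-year window can stay.
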